**Table 7. Compliance by randomised group: GTN and Control.**

Data are number (%).

Period	GTN	Control	Difference (p)
Received first day of treatment	xxx (xxx)	xxx (xxx)	Chi-sq
Received all 2 days treatment	xxx (xxx)	xxx (xxx)	Chi-sq
Received some treatment	xxx (xxx)	xxx (xxx)	Chi-sq

**Table 8. Serious adverse events for GTN in relationship to the study.**

Data are number (%).

SAEs up to day 90					Fatal SAEs up to day 90				
	All	GTN	Sham	Difference (p)		All	GTN	Sham	Difference (p)
Number SAEs	xxx	xxx	xxx		Number SAEs	xxx	xxx	xxx	
Treatment time									
...Before		xxx	xxx (xxx)	BLR	Before		xxx	xxx (xxx)	BLR
...During	xxx	xxx (xxx)	xxx (xxx)	BLR	During	xxx	xxx (xxx)	xxx (xxx)	BLR
...After	xxx	xxx (xxx)	xxx (xxx)	BLR	After	xxx	xxx (xxx)	xxx (xxx)	BLR
Relationship to treatment									
...Not related	xxx	xxx (xxx)	xxx (xxx)	Chi-sq/FET	Not related	xxx	xxx (xxx)	xxx (xxx)	Chi-sq/FET
...Improbable	xxx	xxx (xxx)	xxx (xxx)	-	Improbable	xxx	xxx (xxx)	xxx (xxx)	-
...Possible	xxx	xxx (xxx)	xxx (xxx)	-	Possible	xxx	xxx (xxx)	xxx (xxx)	-
...Probable	xxx	xxx (xxx)	xxx (xxx)	-	Probable	xxx	xxx (xxx)	xxx (xxx)	-
...Definite	xxx	xxx (xxx)	xxx (xxx)	-	Definite	xxx	xxx (xxx)	xxx (xxx)	-

[figure not shown]

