## **SECTION 4. STATISTICAL PRINCIPLES**

### **15 Statistical significance**

#### ***15a Level of statistical significance and p values***

The results of analyses and comparisons will be shown with  $p \leq 0.05$ .

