#### ***15b Confidence intervals***

The results of analyses and comparisons will be shown with 95% confidence intervals.

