**Table D. Descriptive and analytical statistics**

	Nominal	Binary	Ordinal	Continuous	Time to Event
Central tendency	N (%)	N (%)	Median [interquartile	Mean (standard	N (%)

and distribution			range]	deviation)	
Comparisons	Chi-square (2x2, or rxc)	Chi-square (2x2)	Mann-Whitney U	t-test (pooled) change from baseline-Repeat Measures (RM)	
Regression	-	Binary logistic regression (BLR)	Ordinal logistic regression (OLR)	Multiple linear regression (MLR)	Cox proportional hazards regression (CPHR)

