### **25c Analyses of secondary outcomes**

Mechanistic, clinical and safety outcomes will be compared between the treatment groups using binary logistic regression, Cox proportional hazards regression (death), ordinal logistic regression (mRS) or multiple linear regression (BI, TICS, t-MMSE, ZDS, EQ-5D, EQ-VAS, as appropriate (**Table A**), in exploratory analyses.

**25d Covariate adjustment:** Analyses will be adjusted for minimisation covariates including age, stroke severity (NIHSS), time after stroke, systolic blood pressure, and received reperfusion therapy.

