**Table 9. Participants with at least one serious adverse event by organ randomised to GTN versus Sham control.**

Data are number (%), and comparison by binary logistic regression.

	All			Fatal		
	GTN	Control	Difference (p)	GTN	Control	Difference (p)
Number						
Cardiovascular	xxx (xxx)	xxx (xxx)	xxx (xxx, xxx), p=0.xxx	xxx (xxx)	xxx (xxx)	xxx (xxx, xxx), p=0.xxx
Hypotension	xxx (xxx)	xxx (xxx)	xxx (xxx, xxx), p=0.xxx	xxx (xxx)	xxx (xxx)	xxx (xxx, xxx), p=0.xxx
Nervous system	xxx (xxx)	xxx (xxx)	xxx (xxx, xxx), p=0.xxx	xxx (xxx)	xxx (xxx)	xxx (xxx, xxx), p=0.xxx
Haemorrhagic transformation	xxx (xxx)	xxx (xxx)	xxx (xxx, xxx), p=0.xxx	xxx (xxx)	xxx (xxx)	xxx (xxx, xxx), p=0.xxx
Transient ischaemic attack	xxx (xxx)	xxx (xxx)	xxx (xxx, xxx), p=0.xxx	xxx (xxx)	xxx (xxx)	xxx (xxx, xxx), p=0.xxx
Respiratory	xxx (xxx)	xxx (xxx)	xxx (xxx, xxx), p=0.xxx	xxx (xxx)	xxx (xxx)	xxx (xxx, xxx), p=0.xxx
Gastrointestinal	xxx (xxx)	xxx (xxx)	xxx (xxx, xxx), p=0.xxx	xxx (xxx)	xxx (xxx)	xxx (xxx, xxx), p=0.xxx
Genitourinary	xxx (xxx)	xxx (xxx)	xxx (xxx, xxx), p=0.xxx	xxx (xxx)	xxx (xxx)	xxx (xxx, xxx), p=0.xxx
Haematological/immunological	xxx (xxx)	xxx (xxx)	xxx (xxx, xxx), p=0.xxx	xxx (xxx)	xxx (xxx)	xxx (xxx, xxx), p=0.xxx
Metabolic/endocrine	xxx (xxx)	xxx (xxx)	xxx (xxx, xxx), p=0.xxx	xxx (xxx)	xxx (xxx)	xxx (xxx, xxx), p=0.xxx
Musculoskeletal/cutaneous	xxx (xxx)	xxx (xxx)	xxx (xxx, xxx), p=0.xxx	xxx (xxx)	xxx (xxx)	xxx (xxx, xxx), p=0.xxx
Miscellaneous	xxx (xxx)	xxx (xxx)	xxx (xxx, xxx), p=0.xxx	xxx (xxx)	xxx (xxx)	xxx (xxx, xxx), p=0.xxx
Other	xxx (xxx)	xxx (xxx)	xxx (xxx, xxx), p=0.xxx	xxx (xxx)	xxx (xxx)	xxx (xxx, xxx), p=0.xxx
Total	xxx (xxx)	xxx (xxx)	xxx (xxx, xxx), p=0.xxx	xxx (xxx)	xxx (xxx)	xxx (xxx, xxx), p=0.xxx

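### The relatedness test in SAP Table 8 appears to compare the mix of causality labels among SAEs, not the proportion of participants with a treatment-related SAE, and no other table makes that comparison

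*SAP*

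**What the plan says.** SAP section 25c sets the general aim: "Mechanistic, clinical and safety outcomes will be compared between the treatment groups", in exploratory analyses. SAP 15b adds: "The results of analyses and comparisons will be shown with 95% confidence intervals".

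SAP Table 8, "Serious adverse events for GTN in relationship to the study", opens with the number of SAEs by arm, without a percentage or a test. The block headed "Relationship to treatment" then has five rows: not related, improbable, possible, probable and definite. A chi-square or Fisher exact test appears on the first row, with dashes on the other four. The layout is repeated for fatal SAEs. The note begins "Data are number" and promises percentages, but does not say of what. The comparison column holds a p value only.

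SAP Table 9, "Participants with at least one serious adverse event by organ randomised to GTN versus Sham control", counts participants by organ class. It ends with a Total row and uses binary logistic regression, for all and for fatal SAEs. It is not split by relatedness.

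The protocol (Adverse Events, Causality) puts not related and improbable in one category, counted as unrelated, and counts possible, probable and definite as related. The protocol's Assessment of safety plans descriptive summaries of SAEs by treatment received.

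**The concern.** A test over the five labels, computed among SAEs, conditions on an SAE having occurred. Its null hypothesis is that the label mix is the same in both arms given an SAE. The safety question is whether a participant given GTN is more likely than one given sham to have an SAE judged related. The two questions can have opposite answers. If related and unrelated SAEs rise together, the mix does not change. If related SAEs are equal but unrelated ones differ, the mix does change.

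Five separate labels also let the test respond to a shift between not related and improbable, which the protocol treats as one class. If SAEs are the unit, several SAEs in one person enter as independent observations.

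At stake is the only p value in the SAP attached to relatedness, in a trial described as one of feasibility and safety and meant to inform a definitive trial.

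**Working it through.** Table 8 is an empty shell, so there is no plan figure to reproduce.

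**Inputs from the documents.** 60 participants per arm if the target is met (50 + 10, SAP section 9); five labels and one test (Table 8); the related/unrelated grouping (protocol, Causality); significance level 0.05 (SAP 15a), taken as two-sided.

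**Assumed.** All SAE rates and label mixes, since the documents give none. At most one SAE per participant, so clustering plays no part in these results.

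**Worked counts** (order: not related / improbable / possible / probable / definite). The label test is Pearson chi-square = Σ(O − E)²/E over the arm-by-label table, dropping empty labels.

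1. *Proportional excess.* GTN 8/4/8/3/1 (24 SAEs), sham 2/1/2/1/0 (6 SAEs). Expected GTN 8, 4, 8, 3.2, 0.8; expected sham 2, 1, 2, 0.8, 0.2. Chi-square = 0.0125 + 0.05 + 0.05 + 0.2 = 0.3125 on 4 df, p = 0.99 (exact version p = 1.0). Participants with a related SAE: 12/60 = 20% against 3/60 = 5%, a difference of 15 percentage points, Fisher p = 0.025.
2. *No related excess.* GTN 10/0/3/0/0, sham 2/8/3/0/0 (13 SAEs each). Expected per arm 6, 4, 3. Chi-square = 2 × 16/6 + 2 × 16/4 + 0 = 13.33 on 2 df, p = 0.0013 (exact version about 0.001). Related SAEs are 3/60 in both arms, Fisher p = 1. The rejection comes wholly from not related against improbable.
3. *Only related SAEs rise.* GTN 6/4/8/3/1, sham 6/4/2/0/0. Chi-square = 5.1 on 4 df, p = 0.28. Participants with a related SAE: 12/60 against 2/60, Fisher p = 0.008.

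**Simulation.** 4,000 trials per row, so the Monte Carlo standard error is at most √(0.25/4000) = 0.8 percentage points. In the first three rows the label mix is 40/20/25/12/3%. In the others, unrelated SAEs split 2:1 between not related and improbable, and related SAEs split 62.5/30/7.5%. The table gives the percentage of trials with p ≤ 0.05.

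| Scenario (GTN vs sham) | Five-label chi-square | Related vs unrelated among SAEs, Fisher | Participants with a related SAE, Fisher |
|---|---|---|---|
| Any SAE 50% vs 12.5%, same mix | 4.7 | 2.5 | 61 |
| Any SAE 40% vs 10%, same mix | 5.0 | 2.2 | 48 |
| Any SAE 60% vs 20%, same mix | 4.4 | 2.9 | 60 |
| Related 25% vs 5%, unrelated 20% both | 36 | 56 | 85 |
| Related 20% vs 5%, unrelated 20% both | 22 | 40 | 63 |
| Related 25% vs 5%, unrelated 10% both | 29 | 41 | 85 |
| Related 8% both, unrelated 5% vs 40% | 58 | 61 | 2 |
| Related 8% both, unrelated 10% vs 30% | 20 | 24 | 2 |
| Related 8% both, unrelated 5% vs 20% | 22 | 26 | 2 |

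The middle column shows that collapsing the labels to related and unrelated while staying among SAEs does not cure the problem. The denominator has to be participants.

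**The case against.** - *The reading is inferred.* No denominator or unit of analysis is stated, and the treatment-time rows of the same table name binary logistic regression, which needs a yes/no outcome. This stands. But an event count at the head, no row for participants without an SAE, and a single test over the block make the arm-by-label test among SAEs the natural reading.
- *Table 9 covers the worst case.* A reader might infer that a rise in all SAEs would go unnoticed. The documents do not support that: the Total row of Table 9 compares participants with at least one SAE, and Table 8 shows the SAE counts. What remains is that neither table compares participants with a related SAE.
- *The test is not blind.* A reader might infer that it cannot see an excess of related SAEs. That holds only for a proportional rise; when related SAEs alone rise, the test has some power, though much less.
- *Rejection with equal related SAEs is not an error for the null tested.* The mix really does differ in those scenarios. The fault is that the result would be read as a difference in relatedness.
- *The rates are assumed.* Non-fatal SAEs are collected only to day 2, so rates of 12.5-60% may be too high. The direction of the result follows from the conditioning; the percentages do not carry over.
- *Relatedness is not a listed endpoint.* The safety endpoints are any SAE, fatal SAEs and named events, so relatedness should not be called the main safety signal. The comparison is exploratory, the DMC reviews unblinded safety data, and no decision is tied to this p value. All of this limits the severity.

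**Conclusion.** On the natural reading of its layout, Table 8 does not test, and can miss, an excess of treatment-related SAEs, and it can reject when there is none. With 60 per arm and the assumed rates, it rejects in 4-5% of trials under a proportional rise (48-61% for the participant-level test). It has 22-36% power when only related SAEs rise (63-85%). It rejects in 20-58% of trials when related SAEs are equal at 8% (about 2%). The mechanism does not depend on those rates; the sizes do.

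The missing confidence interval is a lesser gap, since SAP 15b already requires one for comparisons. The point is minor: one exploratory p value in a feasibility trial, with counts by label on display and an any-SAE comparison in the next table.

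**What to change.** In SAP Table 8, for all SAEs and for fatal SAEs:

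- Remove the test from the relatedness block. Keep the counts by label as description, and state that they are events and what the percentages are of.
- Add a row for participants with at least one SAE judged possible, probable or definite, over all participants in the arm (n/N, %). Use the safety population by treatment received, and give a risk difference with a 95% confidence interval, labelled exploratory.

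This agrees with the protocol's causality grouping, its descriptive plan for SAEs, the SAP's safety population and SAP 15b. It also removes the problem of repeat SAEs in one person.

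The cost is an edit to a table shell; causality is already assessed for each SAE, so no new data are needed. There is one drawback. Causality is judged in conjunction with treating practitioners, staff who apply patches know the allocation, and an investigator can unblind by lifting the gauze. Labels may therefore be influenced by knowledge of treatment, so the new row should be read beside the any-SAE Total in Table 9. Since the title of Table 9 refers to randomised groups, state which population each table uses so that the two can be compared.

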Outcome measures	
Feasibility outcome
 
 
Recruitment of 100 IS patients, 20 ICH patients
 
 
Mechanistic outcomes
 
 
Blood pressure (BP) and heart rate (HR) over first 2 days
 
Bloods
 
 
Clinical outcomes
 
Day 2
 
 
Impairment
 
 
Discharge or death
 
 
Discharge destination
 
 
Day 90
 
 
Functional outcome: modified Rankin Scale (mRS = primary clinical outcome)
 
Disability (Barthel index, BI), cognition (telephone TICS, MMSE), mood (Zung depression scale, ZDS), quality of life (Euro-QoL EQ-5D and EQ-VAS).
 
 
Safety outcomes
 
 
Serious adverse events (SAEs) up to day 2 (i.e., 48 hours after 1st patch applied; fatal SAEs to day 90.
 
Death
 

Statistical methods	
This is a feasibility trial, and the main analysis will be with descriptive statistics only. Counts will be summarised using N and %, and continuous variables will be summarised using means (standard deviation) or median [interquartile range] depending on their distribution. Mechanistic, clinical and safety outcomes will be compared between the treatment groups using binary logistic regression, Cox proportional hazards regression (death), ordinal logistic regression (mRS) or multiple linear regression (BI, TICS, t-MMSE, ZDS, EQ-5D, EQ-VAS, as appropriate, in exploratory analyses.

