## **Definition of populations analysed**

All available data will be used including overall numbers of patients presenting in clinic and screening data (where available).

Where summaries by treatment group are provided, these will be based on an intention to treat population i.e., according to the treatment the participant was randomised to, with the exception of safety data.

A safety population will be defined to summarise the safety data in this study. Participants will be summarised according to the treatment they received irrespective of randomisation.

Summaries of the proportion of participants who would form a per protocol population in a larger trial, and reasons for exclusion from a per protocol population will be provided, to allow future planning. No data will be summarised on this population.

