Important medical events that may not result in death, be life-threatening, or require hospitalisation may be considered a serious adverse event when, based upon appropriate medical judgment, they may jeopardize the patient or participant and may require medical or surgical intervention to prevent one of the outcomes listed in this definition

All adverse events will be assessed for seriousness, expectedness, and causality:

A distinction is drawn between serious and severe AEs. Severity is a measure of intensity whereas seriousness is defined using the criteria above. Hence, a severe AE need not necessarily be serious.

Serious adverse events are common in stroke; a full list of expected SAEs that are not subject to expedited reporting are given in Appendix K.

As the IMP is administered once and has a short half-life, serious adverse events occurring within the first 2 days will be assessed for seriousness, expectedness, and causality. In addition, fatal SAEs will be reported until day 90.

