### **24c Safety endpoints**

1. By day 2
  - Any serious adverse event.
  - Headache.
  - Infection (pneumonia/chest, urinary tract, other).
  - Hypotension requiring clinical intervention.
  - Hypertension requiring clinical intervention.
2. From day 3 to day 90
  - Any fatal serious adverse event.

Data on stroke recurrence and acute coronary syndrome, termed safety outcome events, will be collected up to day 90.

**24d Units:** Units will be shown in tables.

**24e Calculations/transformations:** Quality of life using UK weightings.

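### SAP Tables 8 and 9 do not match the SAE collection windows: non-fatal SAEs stop at day 2, and the endpoint of any SAE by day 2 has no row tied to that window

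*SAP*

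**What the plan says.** **Collection.** The protocol synopsis sets the safety outcome as "Serious adverse events (SAEs) up to day 2 (i.e., 48 hours after" the first "patch applied; fatal SAEs to day 90". The adverse events section of the protocol agrees: "serious adverse events occurring within the first 2 days will be assessed for seriousness, expectedness, and causality", with fatal events reported on to day 90. SAP 24c lists any SAE under day 2 and, for day 3 to day 90, only "Any fatal serious adverse event". The assessment schedules (protocol, Participant measures; SAP Table C) mark non-fatal SAEs on day 0 after treatment, day 1 and day 2, with no mark at discharge or day 90. Fatal SAEs have their own row, which runs to day 90.

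**Reporting.** SAP Table 8 has two panels, "SAEs up to day 90" and "Fatal SAEs up to day 90". Each is split into Before, During and After treatment, and these terms are not defined. Table 9 is titled "Participants with at least one serious adverse event by organ randomised to GTN versus Sham control". It has an All block and a Fatal block, each with a Total row, and gives no window for either. Table 4's list of events to day 2 names specific events but has no row for any SAE. SAP section 28 (Harms) points to a table and gives no window.

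**Population.** On safety data the protocol says "Participants will be summarised according to the treatment they received irrespective of randomisation". The protocol's Assessment of safety section and the safety population in SAP section 18 also use treatment received.

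**The concern.** A reader of a panel headed as SAEs to day 90 will take it as a 90-day SAE count. It cannot be one, because non-fatal SAEs are not collected after day 2. Table 9 raises the same problem in a form that carries an estimate. Its All columns are compared by binary logistic regression with no stated window, so early events of any kind are pooled with deaths up to three months later. Treatment lasts two days, and the early period bears most directly on the safety of the patch. The SAP names that period as an endpoint but gives it no result row of its own. The trial is meant to inform a definitive study, so a mislabelled SAE figure could be carried into that study's planning and safety case.

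**Working it through.** The plan states no figure to reproduce. The check sets the collection rules beside each table that could carry SAEs, then asks what Table 9's pooled column would measure.

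**1. Windows against tables**
- *Collected:* any SAE from first patch to 48 hours; fatal SAEs to day 90. The synopsis, the protocol endpoint list, the adverse events section, both schedules and SAP 24c agree.
- *Table 8, left panel:* labelled to day 90. On the collection rules it holds any SAE to day 2 plus fatal SAEs to day 90. Non-fatal SAEs are observed for 2/90 = 2.2% of the labelled period.
- *Table 8, During row:* undefined. The protocol's trial configuration puts the second patch on at 09.00 the next day, whatever the time of the first. Time on treatment is therefore not a fixed interval from the first patch and need not equal 48 hours.
- *Table 9, All block:* no window, so the same mixture. Its Total row counts participants and is the nearest thing to the SAP 24c endpoint, but it is not limited to day 2.
- *Table 4:* covers the right period but has no row for any SAE.
- *Table 3:* reports recurrent stroke and acute coronary syndrome at day 90. SAP 24c collects these to day 90 as a separate class of safety outcome events. Nothing says whether such an event after day 2, if serious but not fatal, would also enter Tables 8 and 9.

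**2. Can late deaths drive Table 9's pooled column?**
The documents give no day-2 SAE rate, so this is an illustration with no difference between arms by day 2.

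Inputs:
- Death rates from SAP Table B, GTN vs control: ENOS 12% vs 13%, ENOS-early 8% vs 20%, RIGHT-2 23% vs 19%. That table gives no follow-up time; I treat them as 90-day rates.
- 60 per arm (120 planned, 1:1). Expected deaths per arm = 60 × rate: 7.2 vs 7.8, 4.8 vs 12.0 and 13.8 vs 11.4, or about 15 to 25 in all.
- Assumed: day-2 SAE rate *a* of 5% to 20%, the same in both arms; share *s* of deaths after day 2 of 50% to 100%; late death independent of having had a day-2 SAE.

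Formula: pooled proportion = 1 − (1 − a)(1 − d·s), where d is the arm's death rate.

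Worked case, ENOS-early, a = 10%, s = 80%:
- GTN: 1 − 0.90 × (1 − 0.064) = 15.8%
- control: 1 − 0.90 × (1 − 0.16) = 24.4%
- odds ratio = (0.1576/0.8424)/(0.244/0.756) = 0.58

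Pooled odds ratio over the assumed ranges, with a true day-2 odds ratio of 1:
- ENOS-early rates: 0.46 to 0.78
- ENOS rates: 0.93 to 0.98
- RIGHT-2 rates: 1.08 to 1.23

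Participants counted only because of a late death make up 14% to 81% of those in the column. A few low-*a*, low-*s* combinations are impossible, because deaths by day 2 would exceed all SAEs by day 2; dropping them does not move the ends of these ranges.

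The pooled column can therefore move in either direction through late mortality alone. These values show the mechanism and do not predict ENOS-2's result.

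**The case against.** The strongest reply is that this is a feasibility trial. SAEs are to be described, treatment comparisons are exploratory, the collection rule is the same in both arms, and the true windows are stated elsewhere in the SAP. All of that stands, and it limits the point to reporting.

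Several stronger readings are tempting and are not supported:

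- *A reader might infer that late deaths dilute Table 8's treatment-period comparison.* Table 8 puts logistic regression on the Before, During and After rows and no test on the total number of SAEs. Its other test concerns attribution to treatment, not frequency. Late deaths fall in After. The pooling problem for a frequency comparison belongs to Table 9.
- *A reader might infer that the After row merely repeats the fatal panel.* SAP Table C heads its day-2 column as after treatment and marks non-fatal SAEs there, so After can include non-fatal events.
- *A reader might infer that only deaths can appear after day 2.* That follows from the SAE rules, but recurrence and acute coronary syndrome are collected to day 90 and could meet the SAE definition. The SAP does not say how they are handled.
- *A reader might infer that there is no participant-level SAE count.* Table 9's Total row is one; it lacks a window.

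The protocol's section on reporting adverse events also says that all adverse events will be recorded. Its definitions section says that adverse events in general are not collected, and every specific statement on SAEs stops non-fatal events at day 2. The general sentence does not rescue the 90-day label.

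**Conclusion.** The point holds as a defect in the SAP tables. Table 8's 90-day heading is wrong for non-fatal SAEs. Table 9's All columns, including the Total, mix a 2-day window for any SAE with a 90-day window for fatal SAEs. The endpoint of any SAE by day 2 has no row tied to its window; reading that endpoint as participants with at least one SAE is an interpretation, though the natural one. Table 9's title also conflicts with the rule that safety data follow treatment received.

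No effect size is claimed. The illustration rests on assumed day-2 rates, an assumed timing of deaths and independence, and shows only that late deaths can drive the pooled comparison. The SAP does not rank its SAE tables, so neither should be called the main one. The collected data and the primary feasibility endpoint are unaffected. The tables should be corrected before database lock.

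**What to change.** - **Table 8:** head the left panel *Any SAE, to day 2* and the right panel *Fatal SAEs, to day 90*, with the right panel split into day 0–2 and day 3–90. Define Before, During and After against the time of the first patch and the 48-hour limit, and say what can belong in Before under the protocol's SAE definition.
- **Table 4:** add a row *Participants with any SAE by day 2*.
- **Table 9:** give *Any SAE to day 2* and *Fatal SAE to day 90* as separate, labelled windows. If All were simply cut at day 2 beside an unlabelled Fatal block, Fatal could exceed All; the labels stop Fatal being read as a subset.
- **Population:** present Tables 8 and 9 by treatment received, and retitle Table 9 accordingly.
- **Recurrence and acute coronary syndrome:** state that after day 2 these are reported in Table 3 and are not counted in the SAE tables unless fatal.

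The cost is edits to table headings, short definitions and one added row. No new data and no change to trial conduct are needed.
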